Data Collected: (1) **Baseline Visit:** ICF, HIPAA, medical history, demographics, Vital signs (blood pressure and pulse, height and weight), study questionnaires (ThyPRO Hypothyroid symptoms and Tiredness scales, EQ-5D ThyPRO-39) and blood sample collection (TSH, FT4, lipids). (2) **Telephone Visit 1** (Month 1 +/- 3 days): Adverse event assessment and study medication compliance assessment. (3) **Clinic Follow-up 1** (6-8 weeks post randomization): Vital signs (blood pressure and pulse, weight), study questionnaires (ThyPRO Hypothyroid symptoms and Tiredness scales, EQ-5D), study medication compliance assessment, adverse event assessment and blood sample collection (TSH, FT4, TPO antibodies). (4) **Telephone Visit 2** (Month 3 +/- 3 days): Adverse event assessment and study medication compliance assessment. (5) **Telephone Visit 3** (Month 4 +/- 3 days): Adverse event assessment and study medication compliance assessment. (6) **Telephone Visit 4** (Month 5 +/- 3 days): Adverse event assessment and study medication compliance assessment. (7) **Clinic Follow-up 2** (Month 6 +/- 3 days): Vital signs (blood pressure and pulse, weight), study questionnaires (ThyPRO Hypothyroid symptoms and Tiredness scales, EQ-5D, ThyPRO-39, End of Study survey), study medication compliance assessment, assessment of integrity of blinding, disclosure of study medication assignment to participant, blood sample collection (TSH, FT4, blood lipids), duration of LT4 therapy and return to usual care plan. (8) **Unscheduled Visit:** an unscheduled visit(s) may be performed during the study. The unscheduled visit may be completed by telephone or in-person. Possible reasons for an unscheduled visit include safety assessment (such as lab collection for assessment of possible adverse event), repeat lab collection (test error or result confirmation), early termination (participant, Investigator, or joint decision) and/or study medication resupply.

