Planned Analysis: Initial data analysis will include descriptive statistics for all variables, including assessment of potential outliers and the extent of missing data. If the missing data rate is small, < 5%, and found to be at random, then complete case analyses will be performed; otherwise, multiple imputation strategies will be explored. Data will be presented as frequencies for categorical variables and means (standard deviations) for continuous variables. We will compare characteristics between groups using t-tests for quantitative variables and chi-square tests for categorical variables. For the primary outcome, intervention feasibility, we will calculate participants' willingness to enter the trial (percent of eligible Veterans approached who consented to participate), recruitment rate (number of patients randomized divided by the length of the recruitment period, i.e., from the date that recruitment opened to the date of the last randomization). These measures will shed light on the anticipated acceptability of LT4 discontinuation. Finally, we will calculate completion rate for each arm. Secondary outcomes include changes from baseline to 6 months in the ThyPRO Hypothyroid Symptoms and Tiredness scores, EQ-5D, ThyPRO-39 and blood lipids. We will also assess changes in weight, body mass index, blood pressure,

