and pulse. Analysis of covariance (ANCOVA) models will be employed to analyze these outcomes. Baseline measures and gender will be included in the models as covariates. A one-sided t-test will be used to determine whether the mean ThyPRO Hypothyroid Symptoms and Tiredness scores for the real discontinuation group differ from the mean ThyPRO Hypothyroid Symptoms and Tiredness scores of the sham discontinuation group by no more than 14 points. An  $\alpha$ -level of 0.05 will be used to determine the statistical significance of the non-inferiority test for each ThyPRO domain. Failure to reject the null hypothesis will suggest that the QoL measures in the real discontinuation group, on average, are more than 14 points worse than in the sham discontinuation group. This will be considered as evidence against our conjecture that discontinuation does not negatively affect the QoL of patients with SCH. In addition, analyses comparing groups with respect to adverse event rates will be performed using chi-square tests. Analyses will be based on the intention-to-treat principle. Statistical analyses will be done using SAS 9.4 (SAS Institute, Cary, NC).

*Additional details Analysis Plan:* We will add a Biostatistician to the project. They will be hired through an IPA to work on the project. The Biostatistician will be sent the data set by encrypted email and will use computer software on their laptop (non-VA) to complete the analysis. No name, date of birth or SSN will be included in the data set for analysis. Those data points will remain within the VA protected environment.

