*Sample size estimates:* The overarching goals of this pilot trial are to assess the feasibility of a subsequent, full-scale effectiveness trial and to obtain preliminary estimates of effect sizes. Thus, the pilot needs to be large enough to be informative about the feasibility of recruitment/retention and research procedures and to provide enough information on the efficacy of the intervention to justify and inform the planning of a full-scale trial. The primary endpoints of the full-scale RCT will be the ThyPRO Hypothyroid Symptoms scale and Tiredness scale scores. With an estimated standard deviation of 20 for ThyPRO hypothyroid scale score, from a study of patients with autoimmune hypothyroidism, a sample size of 23 Veterans per group will allow us to achieve 80% power using a 5%  $\alpha$ -level to determine statistical significance for a one-sided t-test; accounting for a drop-out rate of less than 10%, a final sample size of 50 patients will be required. This sample size is adequate both to assess feasibility and to obtain preliminary data on effect sizes.

*Participant Compensation:* Participants will be provided compensation for time and travel expenses as a result of participating in the study. The payments will be distributed as follows: (1) \$50 for completion of Baseline Visit, (2) \$50 for completion of Clinic Follow-up 1 (Month 2), (3) \$50 for completion of Clinic Follow-up 2 (Month 6), and (4) \$100 for completion of all study activities and End of Study survey. The participant will be paid within 4-6 weeks after each clinic visit. Payment will be issued by check or by electronic transfer of funds according to local medical center procedures. The participant name, SSN, address and date of visit are required to process the funds. An Internal Revenue Service (IRS) Form 1099 will be generated using the participant's SSN. On a case-by-case basis, the PI may authorize additional compensation to cover the cost of transportation (public transportation or gas mileage estimate).

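### The missing-data rule for the ThyPRO and EQ-5D scores turns on a condition the data cannot establish, leaves imputation open, and makes no stated use of the 6–8 week scores

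*Combined protocol and SAP*

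**What the plan says.** The rule stands in the Planned Analysis section of the combined protocol and SAP: "If the missing data rate is small, < 5%, and found to be at random, then complete case analyses will be performed". For every other case the section offers only this: "otherwise, multiple imputation strategies will be explored". The section gives no method for judging randomness, no imputation model, no definition of the missing rate (by variable or by participant) and no sensitivity analysis.

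Under Data Collected, Clinic Follow-up 1 at 6–8 weeks includes "study questionnaires (ThyPRO Hypothyroid symptoms and Tiredness scales, EQ-5D), study medication compliance assessment". The Planned Analysis takes change from baseline to 6 months, by ANCOVA with baseline and gender as covariates, and does not mention the 6–8 week scores.

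The test at stake is one-sided: "A one-sided t-test will be used to determine whether the mean ThyPRO Hypothyroid Symptoms and Tiredness scores" in the placebo arm differ from those of the "sham discontinuation group by no more than 14 points". The "level of 0.05 will be used to determine the statistical significance of the non-inferiority test for each ThyPRO domain". The sample size section plans for drop-out, "accounting for a drop-out rate of less than 10" per cent.

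**The concern.** There are three weaknesses.

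- **The condition cannot be met as written.** Observed data cannot separate missing at random from missing not at random. What can be checked is whether missingness is related to observed scores, and with one or two missing values that check is weak.
- **The fallback is open.** If data are judged not at random, the plan turns to multiple imputation, which in its standard form itself assumes missing at random. With no model named, the method would be chosen after the data are seen.
- **The most useful predictor is not used.** For a participant lost after the 6–8 week visit, the score from that visit is likely to be the best guide to the missing Month 6 score.

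The direction matters. The safety section names worsening hypothyroid symptoms as the risk of placebo, and participants may leave at any time. If those who feel worse on placebo are lost, the remaining placebo mean looks better, and in a non-inferiority test that favours the study's conjecture that discontinuation does no harm.

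**Working it through.** **1. Which branch applies.** Counting by participant, 2/50 = 4% meets the 5% limit and 3/50 = 6% does not, so complete cases need at most 2 missing. The plan's own allowance is 50 − 2 × 23 = 4 losses, or 8%, consistent with its stated ceiling. The chance of 3 or more missing is 1 − Σ C(50,x) p^x (1−p)^(50−x) over x = 0, 1, 2:

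- p = 0.08 (assumed): 1 − (0.0155 + 0.0672 + 0.1433) = 0.774
- p = 0.05 (assumed): 1 − (0.0769 + 0.2025 + 0.2611) = 0.46

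Separately, 23 per group does not follow exactly from a margin of 14 and an SD of 20: 2 × 20² × (1.645 + 0.842)² / 14² = 25.2, so 26. This does not affect the present point.

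**2. Error at the margin.** Inputs from the documents: margin 14, one-sided 5%, 25 per arm, and an SD of 20 ("With an estimated standard deviation of 20 for ThyPRO hypothyroid scale score"). Assumed, because the documents give nothing:

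- a true deficit of 14 points at both 6–8 weeks and Month 6;
- all losses in the placebo arm;
- correlations of 0.5 (baseline with 6–8 weeks), 0.5 (baseline with Month 6) and 0.7 (6–8 weeks with Month 6).

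Each scenario was simulated 3,000 times and analysed by baseline-adjusted ANCOVA (gender omitted), with 10 imputations combined by Rubin's rules. The Monte Carlo standard error is √(0.05 × 0.95 / 3000) = 0.4 percentage points at 5%. With no data lost, the same runs gave 4.4% to 5.4%.

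False non-inferiority rate with 2 placebo losses, where complete cases can apply:

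| Loss depends on | Lost from | Complete case | Imputed, baseline only | Imputed with 6–8 week score |
|---|---|---|---|---|
| 6–8 week score | worse half | 6.3% | 6.0% | 4.7% |
| 6–8 week score | worst quarter | 7.1% | 7.3% | 5.4% |
| 6–8 week score | worst two | 8.3% | 8.2% | 4.5% |
| Month 6 score | worse half | 7.6% | 7.3% | 6.6% |
| Month 6 score | worst quarter | 9.7% | 9.7% | 8.2% |
| Month 6 score | worst two | 12.1% | 11.9% | 9.1% |

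With 4 placebo losses the rule sends the analysis to imputation:

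| Loss depends on | Lost from | Imputed, baseline only | Imputed with 6–8 week score |
|---|---|---|---|
| 6–8 week score | worse half | 8.3% | 5.3% |
| 6–8 week score | worst quarter | 10.6% | 5.6% |
| 6–8 week score | worst four | 11.9% | 4.9% |
| Month 6 score | worse half | 10.2% | 7.7% |
| Month 6 score | worst quarter | 17.7% | 13.1% |
| Month 6 score | worst four | 22.6% | 15.0% |

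As a yardstick for the baseline-only model: when the worst four on the 6–8 week score are lost, the estimate is off by 2.54 points with baseline-only imputation and by 2.53 points with no imputation. With the 6–8 week score the error is 0.05 points.

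**3. Other correlations, 2 losses depending on the 6–8 week score.** With 0.60, 0.55 and 0.75, repeat runs put complete-case error at 6.1% to 6.7% under milder selection and 8.4% to 9.4% for the worst two; imputing with the 6–8 week score gives 4.8% to 5.7%. With weaker values (0.5, 0.4, 0.5), the worst-two figure is 6.6%, against 4.6% imputed.

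**4. Would a check notice?** Under the stronger correlations, a t-test of 6–8 week scores, missing against observed, is significant at 0.05 in about 99% of runs when the worst two are lost, but in only 23% to 38% under milder selection.

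**The case against.** The strongest reply is that the rule has two conditions, not one. If its second condition is read as a check of missingness against observed scores, the case with the largest inflation would almost always be seen and sent to imputation; where the check misses, inflation is about one percentage point. This stands as far as it goes. It rules out the reading that the rule as written would nearly double the false non-inferiority rate. It does not make the rule sound: the plan specifies no check, and the branch it leads to has no model.

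A reader might also quote complete-case error rates for four losses. Four of 50 is 8%, and the plan does not allow complete cases there.

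The loss pattern is also unfavourable by construction. With equal drop-out in both arms, exactly two losses, both on placebo, has probability 0.143 × (25 × 24)/(50 × 49) = 3.5% at 8% drop-out, and 0.261 × 0.245 = 6% at 5%. Losses driven by symptoms would not be equal by arm, but nothing in the documents says how unequal.

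The plan does limit missing data. Participants who stop study medication are asked to stay for visits and questionnaires, and payment is attached to Month 6 and to full completion. Staying is voluntary and may be partial, so this reduces the problem without removing it.

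Finally, the primary outcome is feasibility and the ThyPRO test is secondary. That lowers the stakes. Yet the sample size is justified by this test, and the two scales are the intended primary endpoints of the full-scale trial.

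**Conclusion.** The concern holds at moderate strength. The complete-case condition cannot be established from the data, the alternative is unspecified, and the 6–8 week scores have no stated role. With two placebo losses that depend on the 6–8 week score, one-sided error is about 6% under mild selection and 7–9% in the extreme case, where a check would probably divert the analysis. With three or more missing (77% at an assumed 8% drop-out, 46% at 5%), the outcome depends on an imputation model not yet chosen; a baseline-only model would remove almost none of the bias.

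Two further inferences go too far. The plan does not exclude the 6–8 week scores from imputation; it is silent. Nor would using them cure every case: if loss depends on the unseen Month 6 score, error stays at 6.6% to 9.1% with two losses and 7.7% to 15.0% with four. All these sizes rest on assumed correlations, selection and one-sided loss. The direction of the bias and the gap in the plan are firmer than any single figure.

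**What to change.** Replace the rule with one prespecified analysis for ThyPRO Hypothyroid Symptoms, Tiredness and EQ-5D, used whatever the missing rate. Either of these would serve:

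- a repeated-measures mixed model with baseline, 6–8 week and Month 6 scores, adjusted for gender, with the 14-point contrast for the two ThyPRO scales taken at Month 6; or
- multiple imputation with arm and the 6–8 week score in the imputation model along with baseline and gender, followed by the planned ANCOVA.

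Add one delta-adjusted sensitivity analysis that worsens the imputed placebo scores by amounts fixed in advance, because the 6–8 week score repairs the bias only in part if loss depends on unseen Month 6 scores.

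The cost is a few sentences in the analysis plan and modest extra programming, with no new data or visits. ThyPRO-39 and lipids have no 6–8 week value and keep ANCOVA with imputation.

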**Randomized Clinical Trial (RCT) protocol**  
**5/30/2023**

**Principal Investigator (PI):**  
**[name], MS**

**NCT 04288115**

**Aim. Evaluate the feasibility of LT4 discontinuation among Veterans with SCH and determine the changes in quality-of-life measures, treatment burden, and adverse events.**

Design: Double-blind, placebo-controlled randomized clinical trial

Performance site: CAVHS

Participants: Fifty veterans with LT4-treated SCH will be randomized to either (1) continue current dose of LT4 [pre-study dose] or (2) placebo. Up to 150 veterans will need to sign consent and HIPAA authorization to reach 50 randomized participants due to the anticipated screen failure rate. The screen failure rate accounts for participants whose baseline lab results (TSH, FT4 and LDL) are out of study range. Participants will be identified from CDW/Strategic Management (Aim 1) and referrals from CAVHS providers (including Primary Care or Endocrine clinic providers).

Exclusion Criteria: (1) TSH > 10 mIU/L (at any point), (2) LT4 dose more than 75 mcg daily, (3) use of antithyroid medications, amiodarone, tyrosine kinase inhibitors or lithium, (4) history of thyroidectomy or radioactive iodine therapy, (5) LT4 suppressive therapy for thyroid cancer, goiter or inflammation, (6) pregnancy or plans for pregnancy in the next 6 months, (7) an unstable medical condition that would jeopardize safety or interfere with study participation, (8) hospitalization for major illness within the previous 4 weeks, (9) severe hypothyroidism-related symptoms, (10) strong family history of hypothyroidism, (11) severe dyslipidemia, (12) acute coronary artery syndrome, acute myocarditis, or pancarditis or stroke within the previous 12 months, (13) Grade IV New York Heart Association (NYHA) heart failure, (14) receiving services from hospice, (15) lack of decision-making capacity, (16) terminal medical condition for which life expectancy would be less than 6 months, (17) not willing to stop LT4, (18) self-reported non-adherence to LT4 therapy and (19) abnormal TSH at time of screening for participation (assessed during Baseline Visit). Pregnancy testing will be performed for females of child-bearing potential that sign consent to participate in the study. The results will be reviewed prior to randomization.

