Recruitment: We will send an **IRB-approved opt-out letter** to eligible veterans identified from CDW/Strategic Management or referral from CAVHS provider. The Principal Investigator (PI) has presented the study background, goals, and procedures to endocrinologists and primary care clinicians at CAVHS, answered questions, and got feedback from them (Development phase). A post-presentation poll of primary care physicians showed that 75% felt that LT4 discontinuation was acceptable in patients with SCH and 97% were comfortable with randomization of their eligible patients in the study. All endocrinologists felt that LT4 discontinuation was acceptable in patients with SCH and were comfortable with randomization of their eligible patients in the study. Clinicians were informed that Veterans under their care may be invited to participate and that those Veterans may want to discuss participation with their clinicians prior to enrolling. Before beginning to recruit, we will repeat the presentation to CAVHS clinicians who might prescribe LT4, including primary care, medicine, and endocrinology service clinicians, to refresh their memories and ensure that we reach clinicians new to CAVHS. In addition, an email with materials describing the study will be sent to clinicians who miss the presentation. Clinicians will be invited to contact the PI if they have questions or concerns about the study. The PI will utilize the Medicine and Primary Care quarterly conference to update clinicians. Study staff will send up to 100 IRB-approved opt-out letters weekly until all eligible veterans identified are sent the letter or 50 veterans are randomized (whichever occurs first). The pool of potential participants will be identified from CDW/Strategic Management and referrals from CAVHS providers. Women and minorities will be included in the study in proportion to their presence among CAVHS patients. We will submit and get approval for a **telephone script**. The designated study staff will call potential participants, with varying lengths of LT4 therapy, that do not opt-out (after at least two weeks from the mail date of the opt-out letter) and use the IRB-approved telephone script to guide the conversation.

Consenting: Written ICF and HIPAA will be obtained by the designated study staff prior to any study activities.

Intervention: (1) Continue current dose of LT4 [control or “sham discontinuation”] or (2) placebo [intervention or “real discontinuation”]

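### The recruitment rate stops its clock at the last randomization, so it is overstated if recruitment ends short of 50

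*Combined protocol and SAP*

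**What the plan says.** Planned Analysis opens the feasibility measures with "For the primary outcome, intervention feasibility, we will calculate participants' willingness to enter the trial" and then adds the recruitment rate, defined as the "number of patients randomized divided by the length of the recruitment period". The period itself is specified as running "from the date that recruitment opened to the date of the last randomization". A completion rate for each arm follows.

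Under Recruitment, letters go out weekly "until all eligible veterans identified are sent the letter or 50 veterans are randomized (whichever occurs first". Telephone contact with those who have not opted out comes "after at least two weeks from the mail date of the opt-out letter". On sources, the same section states: "The pool of potential participants will be identified from CDW/Strategic Management and referrals from CAVHS providers".

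The Participants paragraph expects heavy screening loss: "Up to 150 veterans will need to sign consent and HIPAA authorization to reach 50 randomized participants". The sample size section says that one goal of the pilot is to "assess the feasibility of a subsequent, full-scale effectiveness trial".

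No section defines a date on which recruitment closes, brings time after the last randomization into the denominator, or sets an acceptable value for the rate.

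**The concern.** The end of the observation period is fixed by the event being counted. Time spent recruiting without success counts if a randomization follows it and is dropped if none does. The rate as written can therefore equal the rate measured to the close of recruitment, or exceed it, but it can never fall below it.

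This matters when the mailed pool is used up before 50 are randomized, an outcome that the mailing rule allows for. Work would still continue after the last letter: the two-week wait, the calls, consent in person, and the laboratory review that precedes randomization. At the stated ceiling of 150 consents, 150 − 50 = 100 consented Veterans, or two in three, would not be randomized. It is therefore plausible that some effort after the last success yields nothing.

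The pilot is meant to inform a larger trial. A rate that flatters recruitment only when recruitment has fallen short is an unhelpful planning figure.

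**Working it through.** The plan states no expected rate or recruitment length, so there is no figure of its own to reproduce. From the documents come the definition of the rate, the target of 50, the two conditions that end mailing, and the minimum two-week lag before calls. Everything else below is an assumption.

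**General formula.** Let n be the number randomized, T the time from opening to the last randomization, and L the time from then until recruitment closes.

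- Rate as written: n / T
- Rate to close: n / (T + L)
- Overstatement: (n / T) ÷ (n / (T + L)) − 1 = L / T, whatever n is

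Overstatement for assumed T and L, in months:

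| T | L = 0.5 | L = 1 | L = 3 | L = 6 |
|---|---|---|---|---|
| 12 | 4.2% | 8.3% | 25.0% | 50.0% |
| 18 | 2.8% | 5.6% | 16.7% | 33.3% |
| 24 | 2.1% | 4.2% | 12.5% | 25.0% |

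For example, with n = 40 and T = 18 the written rule gives 40/18 = 2.22 per month. Run to close, the rate is 40/18.5 = 2.16, 40/19 = 2.11, 40/21 = 1.90 or 40/24 = 1.67 for the four tails.

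**What tail to expect.** The table treats L as known. Two accrual patterns show what L might be on average when recruitment closes with n below 50.

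1. *Steady accrual to a fixed close.* The n randomization times are uniform over the window, and the expected ratio of window length to last randomization time is n / (n − 1). For n = 30 this is 30/29, an overstatement of 3.4%. For n = 40 it is 40/39, or 2.6%.
2. *Accrual falling linearly to zero at the close*, as a simple picture of a depleting pool. In 100,000 simulated trials for each n over an 18-month window, the mean overstatement was 20% for n = 30 (median 18%, 5th to 95th percentile 4% to 45%) and 17% for n = 40 (median 15%, 4% to 37%). The ratio does not depend on the window length.

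**When 50 are reached.** If the 50th randomization closes recruitment, L = 0 and the two definitions agree. Stopping on a success carries a small bias of its own under steady accrual, 50/49 − 1 = 2.0%, which either definition shares.

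**The case against.** The strongest reply is that the effect may be trivial. Under steady accrual the expected overstatement at n = 40 (2.6%) is hardly more than the 2.0% present when the target is met. Both are small beside the sampling error of the count itself: 1/√40, or about 16%. A material difference requires accrual to fade before the close, which the documents neither state nor quantify. The only interval given is the wait of at least two weeks, and that by itself points to a tail of weeks. This stands as a limit on size. It does not remove a bias that can run in only one direction.

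A second reply is that the Recruitment section gives a rule for stopping letters and does not say when recruitment closes, and that provider referrals have no end date. That is correct. It means that a close has to be defined, for both sources, before the rate can be corrected.

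A third is that a shortfall would be visible anyway. The number randomized would be below 50, and the willingness measure still counts Veterans approached in the tail. This also stands, and the completion rate is likewise untouched. Only the recruitment rate is affected.

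**Conclusion.** The point holds as a conditional defect in one component of the primary outcome. If recruitment ends short of 50, the written denominator omits the time after the last randomization and the rate is overstated by L / T. The size cannot be computed from the documents. It is about 2–3% under steady accrual and roughly 15–20% on average under the assumed linear fade. If 50 are randomized, there is essentially no difference.

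A reader might infer three stronger things that the documents do not support:

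- **That the overstatement is known to be large, say 25%.** Such a figure needs a recruitment length and a tail that the plan does not give.
- **That the rate is exactly right on success and materially wrong on failure.** Under steady accrual the two cases differ by less than one percentage point at n = 40 (2.6% against 2.0%).
- **That the full-scale trial would be given too few sites or too short a recruitment period.** The plan links the pilot to that trial but does not say this rate will set either quantity. With no feasibility threshold, no decision can be shown to flip.

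**What to change.** In Planned Analysis, end the recruitment period at the date recruitment closed, defined as:

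- the date of the 50th randomization; or
- if 50 is not reached, the date on which the study stops approaching and screening Veterans from both the mailed pool and provider referrals. This can be the date the last approached Veteran is resolved or a stated administrative closing date.

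For the second ending, state when referrals close and when a Veteran who cannot be reached counts as resolved, since the Recruitment section gives no limit on call attempts. An administrative closing date is the simpler choice. Report the last-randomization date and which ending applied, so that readers can see the tail.

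The cost is modest. A closing date has to be recorded prospectively; the documents mention electronic study logs and minuted weekly meetings that review recruitment, either of which could hold it, but they describe no dedicated record of final dispositions. The rate will be less favourable if 50 is not reached and essentially unchanged if it is.

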Randomization Scheme: 1:1, a randomized block design will be implemented to ensure group sizes are equal. Block sizes of 2, 4, and 6 will be used. In addition, randomization will be stratified by participant's pre-study dose of LT4.

Blinded Person(s): PI, Co-Investigators (Drs. [name], [name]), Research Coordinator/Study Staff (SC), Participant, participant's other clinicians (routine care), Biostatistician, Safety Monitor

Unblinded Person(s): [name] (Co-Investigator and Research Pharmacist), [name] (Research Staff and Research Pharmacy), [name] (Research Staff and Pharmacist)

Study Medication Blinding Procedure: The brand of LT4 to be used in this study will be Synthroid® tablets of 25 mcg, 50 mcg, and 75 mcg (AbbVie Inc). The study drugs (LT4 and placebo) will be sourced, assembled, and packaged by the CAVHS Research Pharmacy. Over-encapsulation will be achieved using a capsule filler and will ensure that capsules are kept as small as possible for the ease of swallowing (DB capsules gelatin size AA, color: White Opaque, manufacturer: Capsugel).

Study Medication Dosing: Participants will be instructed to start the study medication the day after randomization. The study medication will be taken orally once a day. A two-month supply of study medication will be provided to the participant at (1) Baseline, (2) around the time of Clinic Follow-up 1, and (3) around the time of Telephone Visit 3 (Month 4). Study medication may also be provided (in-person or by mail) at an unscheduled visit for reasons such as loss of study medication or resupply.

Source of Information: CAVHS veterans

Use of Information: Evaluate the feasibility of LT4 discontinuation among veterans with SCH and determine changes in quality-of-life measures, blood lipids and adverse events.

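### The 14-point non-inferiority decision is not tied to the baseline-adjusted ANCOVA, and the dose stratifier is not named in the model

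*Combined protocol and SAP*

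**What the plan says.** The Randomization Scheme section says that "randomization will be stratified by participant's pre-study dose of LT4". Under Planned Analysis, the secondary ThyPRO outcomes are defined as changes from baseline to 6 months and are to be analyzed by ANCOVA. On covariates the section says "Baseline measures and gender will be included in the models as covariates". Dose is not named, although baseline measures could be stretched to cover it.

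The same section then introduces the decision rule: "A one-sided t-test will be used to determine whether the mean ThyPRO Hypothyroid Symptoms and Tiredness scores for the real discontinuation group differ" by no more than 14 points, at an α of 0.05 for each scale. It does not say whether this test uses the ANCOVA treatment contrast, raw Month 6 means or mean changes. Failure to reject is to be read as "evidence against our conjecture that discontinuation does not negatively affect the QoL of patients with SCH".

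The only analysis principle given is "Analyses will be based on the intention-to-treat principle". Three sections (Compliance and Withdrawal, Study Medication Discontinuation Criteria, Safety Considerations) allow participants to stop study medication, possibly go back to LT4, and stay in follow-up.

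**The concern.** A decision rule should lead two analysts with the same data to the same verdict. Here one could run a two-sample t-test on Month 6 scores, another a t-test on changes, and a third the treatment contrast from the ANCOVA, and each could claim to have followed the plan. All three are valid under randomization, so the issue is precision and fixing the choice before the data are seen.

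The missing stratifier adds to this. Balancing the arms on dose makes the treatment difference less variable if dose predicts the score, but a model without dose does not credit that in its standard error.

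The ThyPRO scales are secondary in this feasibility pilot, which limits the stakes. They matter because the pilot is meant to inform a larger trial, of which the Sample size estimates section says: "The primary endpoints of the full-scale RCT will be the ThyPRO Hypothyroid Symptoms scale and Tiredness scale scores".

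**Working it through.** **Inputs from the documents.** Margin 14 and one-sided α 0.05 (Planned Analysis); SD 20 and 23 per group (Sample size estimates); 1:1 allocation stratified by dose (Randomization Scheme).

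**Assumptions, because the documents give no figure.** True difference 0; correlation r between baseline and Month 6 scores of 0.3 to 0.6; three dose strata, inferred from the three tablet strengths; 15% in the smaller gender group.

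**The plan's own figure.** SE = 20 × √(2/23) = 5.90, so the noncentrality is 14/5.90 = 2.37. With 44 degrees of freedom the critical value is 1.680, and noncentral-t power is 75.6%, not the stated 80%. Reaching 80% at these inputs takes 26 per group (80.1%). This shortfall is a separate matter. It matters here because the sample size rests on a t-test with a raw SD and no baseline correlation.

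**Three readings of the same test.** For changes, SD = 20 × √(2(1 − r)), which gives 23.7, 21.9, 20.0 and 17.9 at r = 0.3, 0.4, 0.5 and 0.6. For ANCOVA, the residual SD is 20 × √(1 − r²), which gives 19.1, 18.3, 17.3 and 16.0. ANCOVA power was simulated so that chance imbalance in baseline and gender is included.

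| Assumed r | t-test, Month 6 scores | t-test, changes | ANCOVA, baseline and gender |
|---|---|---|---|
| 0.3 | 75.6% | 63% | 77% |
| 0.4 | 75.6% | 69% | 80% |
| 0.5 | 75.6% | 76% | 84% |
| 0.6 | 75.6% | 83% | 89% |

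At r = 0 ANCOVA has about 74%. On the same simulated data, the unadjusted and ANCOVA verdicts differ in about 9% of trials at r = 0.3, 14% at r = 0.5 and 18% at r = 0.6.

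The score-or-change question disappears inside ANCOVA. With baseline as a covariate, modelling the change or the Month 6 score gives the same treatment contrast and standard error.

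**Dose stratum.** If dose is unrelated to the score, adding two stratum terms costs 0.1 to 0.6 point of power. With an assumed 10-point step per dose level, it gains about 0.5 point where baseline carries the same step and up to about 5 points where only Month 6 does. Under that step, the error rate at a true difference of 14 is 3.2% to 4.8% for ANCOVA without the stratum and 4.9% to 5.1% with it. Omission is therefore conservative.

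**LT4 restarts (illustrative).** Suppose staying off LT4 costs 14 points, and a fraction f of the placebo arm restarts and recovers a share c of that. The intention-to-treat difference is 14 × (1 − f × c). At f = 0.2:

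- c = 1: difference 11.2, and the t-test declares non-inferiority 12% of the time.
- c = 0.5: difference 12.6, and 8%.
- c = 0: difference 14, and 5%.
- Restarters score 7 points worse (c = −0.5): difference 15.4, and 3%.

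The documents give neither f nor c.

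**The case against.** The best reply is that the test sentence follows directly on the ANCOVA sentences, so a one-sided t-test of the ANCOVA treatment contrast is a natural reading. It is a reasonable reading, but the text does not state it. The sentence speaks of group mean scores, and the sample size uses a raw SD. If that reading is intended, the fix is a single clause.

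A second reply is that nothing in the documents links dose to ThyPRO, so the stratum term is a matter of taste. The gain is indeed hypothetical. Still, the trial already randomizes within dose, and the term costs almost nothing.

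A reader might go further and infer that restarts make the intention-to-treat test falsely favour non-inferiority. The documents do not support that. Intention-to-treat validly answers whether a policy of discontinuing, with restart if needed, is non-inferior. If that policy's effect is 11.2 points, declaring it within 14 is correct. The result is false only for the different question of never restarting, and then only under assumed restart and recovery.

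Nor can one conclude that restart timing goes unrecorded. The stop of study medication is documented, compliance is assessed throughout, and the Month 6 visit records "duration of LT4 therapy and return to usual care plan". The source documents that might hold a restart date are not part of this text.

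**Conclusion.** The point stands as a gap in specification: the test that decides non-inferiority is not identified, and the stratifier is not named in the model. The choice moves power between roughly 63% and 89% over the assumed r of 0.3 to 0.6, and changes the verdict between the unadjusted and ANCOVA tests in about 9% to 18% of simulated trials. These figures assume SD 20, 23 analyzed per arm and no true difference.

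It would be wrong to infer an inflated error rate from the missing stratum, since the test is conservative if dose predicts the score. It would also be wrong to call intention-to-treat invalid. What remains on restarts is minor: the conjecture is worded about discontinuation itself, while the analysis estimates a strategy that permits return to LT4. The size and direction of any dilution are unknown because no restart rate is given.

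This should be changed before analysis, but it does not threaten the primary feasibility outcome.

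**What to change.** For each ThyPRO scale, compute the upper one-sided 95% confidence bound for the treatment difference (discontinuation minus continuation, with higher scores meaning worse) from an ANCOVA of the Month 6 score on baseline score, gender and pre-study dose stratum. Declare non-inferiority if the bound is below 14. Name this as the only decision test, and add dose stratum to the other ANCOVAs.

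The cost is a few lines in the analysis plan and no new data. The price in power is about 2 points (75.6% to about 74%) if baseline is uncorrelated with Month 6, plus at most about 0.6 point for the stratum if dose is irrelevant.

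As a minor addition, keep intention-to-treat as the main analysis, state that it estimates the discontinue-and-restart-if-needed strategy and not continuous time off LT4, and report LT4 restarts by arm.

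A model that excludes placebo-arm scores after restart should be left out or kept as optional and exploratory. It drops post-randomization data from one arm only. In simulation with 20% restarting, half recovery and restart correlated 0.5 with Month 6 symptoms, it declared non-inferiority at a true harm of 14 in 11% of trials, against 8% for intention-to-treat ANCOVA.
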